9. STUDY EVALUATIONS

9.1. Study Procedures

9.1.1. Overview

The TIME AND EVENTS SCHEDULE summarizes the frequency and timing of immunogenicity and safety measurements applicable to the study.

Evaluation of the safety/tolerability and immunogenicity of the vaccine regimens will include laboratory assessments, physical examinations by clinical staff, and subject reports on signs and symptoms following vaccinations. Additional unscheduled study visits may be required if in the investigator's opinion, further clinical or laboratory evaluation is needed.

Subjects will be provided with a thermometer, ruler, and subject diary to measure and record body temperature and solicited local (at injection site) and systemic events.

The diary includes instructions how to capture the data and grading scales to assess severity of the symptoms. The study staff is responsible for providing appropriate training to the subject to avoid missing or incorrect data. The diary card will be reviewed by the study personnel at visits indicated on the TIME AND EVENTS SCHEDULE. If the diary card review is missed, the diary card will be reviewed in the following visit. If a participant misses a vaccination, the diary covering the period after the missed vaccination does not have to be filled in.

From screening to the final main study visit at Week 72, the total blood volume to be collected from each subject will be approximately 1,200 mL. The total blood volume to be collected during the LTE phase (Group 1 and Group 2) in case the subject does not receive the boost vaccination will be approximately 470 mL over a 3-year period. In case subjects receive the boost vaccination, the total blood volume collected from the start of the LTE phase until 12 months post late boost will be approximately 1,201 mL. For subjects followed-up to 24 months post late boost, an additional 145,5 mL of blood will be collected. The total blood volume to be collected is considered to be within the US Department of Health and Human Services (HHS) Office for Human Research Protections (OHRP), and US Food and Drug Administration (FDA) guidelines of 550 mL in any 8-week period. Volumes for humoral immunogenicity testing will be approximately 20 to 30 mL/visit and for cellular immunogenicity testing approximately 50-102 mL/visit except for the Visit 22c (subjects who received the late boost vaccination), during which 200 mL of blood will be collected.

Repeat or unscheduled samples may be taken for safety reasons or for technical issues with the samples.

9.1.2. Visit Windows

The maximum screening period is 6 weeks.

For the study visits, following windows will be allowed as indicated:

- Visit 3: Day 15 ± 5 days
- Visit 4: Day 29 ± 5 days
- Visit 5: Day 85 -1 week, +3 weeks (second vaccination)
- Visit 6*: Visit 5 + 14 days (Day 99) ± 5 days
- Visit 7*: Visit 5 + 28 days (Day 113) \pm 5 days
- Visit 8: Day 169 -1 week, +3 weeks (third vaccination)
- Visit 9*: Visit 8 + 7 days (Day 176) ± 1 day
- Visit 10^* : Visit 8 + 14 days (Day 183) ± 5 days
- Visit 11*: Visit 8 + 28 days (Day 197) \pm 5 days
- Visit 12: Day 253 ± 5 days
- Visit 13: Day 337 -1 week, +3 weeks (fourth vaccination)
- Visit 14*: Visit 13 + 14 days (Day 351) \pm 5 days
- Visit 15*: Visit 13 + 28 days (Day 365) \pm 5 days
- Visit 16: Day 421 ± 3 weeks
- Visit 17: Day 505 ± 3 weeks
- Visit 18 to 21 inclusive and Visit 23/Visit 23a*: Days 673 (Week 96), 841 (Week 120), 1009 (Week 144), 1177 (Week 168), and 1513 (Week 216) ± 4 weeks
- Visit 22/Visit 22a: Day 1345 (Week 192) -4 weeks/+4 months
- Visit 22b*: Visit 22a + 3, 7 or 14 days** (Day 1348 [-1/+2 days], 1352 [± 3 days] or 1359 [± 3 days]; Week 193)
- Visit 22c*: Day 1373 ± 2 weeks (Week 196)
- Visit 22d*, 24*, and 25* (optional visit): Days 1429 (Week 204), 1513 (Week 216), 1681 (Week 240) and 2017 (Week 288)

The visit window for the optional vector shedding assessments will be ± 1 day for every visit. For those vector shedding visits that are also included in the general study schedule (Visit 3 and 4), the ± 1 day window will apply instead of the general ± 5 day window listed above.

*If a subject is not vaccinated on the given day of vaccination, the timings of the visits 1, 2 and 4 weeks post-vaccination of the main study and the Visits 22b, 22c, 22d, 23a, 24, and 25 following late boost vaccination (see TIME AND EVENTS SCHEDULE) will be determined relative to the actual day of vaccination.

** Subjects will be divided into three groups: the first 20 enrolled subjects will have the Visit 22b 7 days post late boost, the next 20 enrolled subjects 3 days post late boost and the remainder of the subjects 14 days post late boost.

If a subject cannot be vaccinated within the allowed window, then that vaccination should not be administered. However, if the window is missed due to a study pause (see Section 11.9) or a special situation such as a pandemic (see e.g. Section 18, COVID-19 APPENDIX: GUIDANCE ON STUDY CONDUCT DURING THE COVID-19 PANDEMIC), vaccination will be assessed on a case-by-case basis upon discussion between investigator and sponsor. If a subject misses more than 1 study vaccination, he/she will be withdrawn from further study vaccination (see Section 10.2).

For the LTE and late boost extension phases (from Week 72 onwards): If a visit can't be scheduled within the allowed window, it will be assessed on a case-by-case basis upon discussion between investigator and sponsor whether this visit can still be performed.

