		•	Cluster of differentiation (CD)4+ and CD8+ T-cell functionality (% cells producing ia, IFN γ , interleukin 2 (IL-2), IL-4, tumor necrosis factor α [TNF α]).
		•	T-cell development with emphasis on follicular helper T-cells and memory differentiation. ^a
Ex	ploratory (applicable to main study, LTE and la	te bo	post vaccination)
•	To explore whether the adenovirus serotype 26 (Ad26) vector is shed after vaccination.	•	Polymerase chain reaction (PCR) positive for Ad26 sequences (urine and mid-turbinate swab).
•	To explore Ab functionality (other than phagocytosis).	•	Ab functionality evaluation (such as Ab-dependent cellular cytotoxicity [ADCC], Ab-dependent complement deposition [ADCD]; excluding phagocytosis (ie, Ab-dependent cellular phagocytosis [ADCP]).
•	To explore Ab Fc characterization.	•	Ab Fc (sub)typing.
•	To explore T-cell and Ab epitope mapping.	•	Epitope mapping of Ab to Env and T-cell responses to Gag/Pol/Env (PTE and vaccine peptide pools).
•	To explore gene expression patterns using PBMCs.	•	Regulation of genes (or clusters) that predict specific immune responses and human leukocyte antigen (HLA) typing.
•	To explore B-cell responses.	•	Ab-producing B-cells and characterization of B-cell memory development.
•	To explore immune responses against the viral vector.	•	Ad26 nAbs (titer).
•	To explore the social impact of participation in an HIV-vaccine study for subjects via a social impact questionnaire.	•	Social impact.
•	To explore durability of the immune responses to the vaccine regimens in the groups selected for the Long-term Extension (LTE) phase.	•	Available samples from time points during the LTE phase will be used for determination of long-term durability of the immune responses.

In addition, the following exploratory objectives are applicable to the late boost vaccination only:

Objectives	Endpoints
• To assess Env-binding Ab responses following late boost vaccination approximately 3 years after receiving the 4 th vaccination of the primary vaccination series.	• Env-specific binding Abs [ELISA] at 3, 7 or 14 days and 28 days post late boost vaccination (titers and breadth).

^a The follicular helper T-cells and memory differentiation was included as secondary objective for the main study. Due to difficulty qualifying the assay for these specific markers, these T-cell responses will be considered as an exploratory objective for the late boost vaccination.

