- ¹¹ Solicited local and systemic signs and symptoms will be recorded by the subject in the diary and solicited local and systemic AEs recorded in the CRF for 7 days after boost vaccination; unsolicited AEs will be recorded from signing of ICF addendum for boost vaccination onwards until 28 days after boost vaccination; SAEs and AESIs of confirmed HIV infection will be recorded from signing of the initial ICF of the main study onwards until the end of the study. Applicable from the time of local regulatory approval of protocol amendment 5 onwards: AESIs of TTS (including potential AESIs) are to be reported to the sponsor until 6 months after the late boost vaccination. In case of a potential AESI of TTS, a serum sample should be obtained to test for anti-PF4 at the local laboratory or substitute local laboratory, if possible; repeat testing may be requested for confirmation upon sponsor discretion. A test for anti-PF4 will also be performed on a stored pre-vaccination sample, if possible.
- ¹² Observation at the study site for at least 30 minutes for presence of any acute reactions and solicited events.
- ¹³ In case the diary was not completed (7 days post-boost) at the time of Visit 22b.
- ¹⁴ Approximately 6 months post Visit 24, the investigator or study-site personnel will have a (remote) follow-up communication with subjects consenting to the 24-month follow-up (by email, telephone, or visit; according to the subject's preference) to collect information on occurrence of any SAEs.
- 15 Visit 25 is an optional visit. Visit 24 and Visit 25 will be the final visit for subjects who, respectively, do not consent and subjects who consent to the 24-month follow-up.
- ¹⁶ For those subjects who are unable to continue participation in the study, an exit visit will be conducted as soon as possible.
- ¹⁷ If a visit can't be scheduled within the allowed window, it will be assessed on a case-by-case basis upon discussion between the investigator and the sponsor whether this visit can still be performed. Note that 1 month should be interpreted as 30 days and 1 week as 7 days; hence, the visit window for visit 22a ought to be interpreted as -28 days/+120 days.

ABBREVIATIONS AND DEFINITIONS

Ab antibody Ad adenovirus

Ad5 adenovirus serotype 5 Ad26 adenovirus serotype 26

ADCC antibody-dependent cellular cytotoxicity
ADCD antibody-dependent complement deposition
ADCP antibody-dependent cellular phagocytosis

AE adverse event

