In addition to an HIV-risk assessment (see Attachment 2), counseling related to avoidance of HIV infection, pre- and post-HIV-test counseling, and contraceptive counseling will be provided to all subjects (men and women). If the vaccination occurs on the same day as the screening HIV risk assessment, contraceptive counselling, and pre-dose counselling on HIV will only be performed once.

Subjects will complete a social impact questionnaire (Attachment 4).

Subjects will have a follow-up clinic visits approximately 3, 7 or 14 days post boost (Visit 22b [Week 193]; first 20 subjects 7 days post late boost, next 20 subjects 3 days post late boost and the remainder of the subjects 14 days post late boost). This visit will include the recording of all concomitant medications and AEs (including SAEs, AEs leading to treatment discontinuation, and AESIs [confirmed HIV infection and TTS]) and review of the diary for 7 days post-vaccination (day of vaccination and the subsequent 7 days). Samples will be collected for humoral and cellular immunogenicity assays.

Subsequent follow-up visits will occur 1 (Visit 22c [Week 196]), 3 (Visit 22d [Week 204]), 6 (Visit 23a), 12 (Visit 24), and, optionally (separate consent to be provided), 24 months post late boost (Visit 25), calculated from the actual day of vaccination. Assessments during these visits include the recording of concomitant medications: all concomitant medications until 28 days post vaccination and from then onwards, concomitant medication given in conjunction with an SAE or AESI of TTS, any chronic or recurrent use of immunomodulators/suppressors, oral or parenteral corticosteroids, any allowed vaccination and/or any HIV prevention medication, including any COVID-19 vaccination. Solicited AEs will be recorded until 7 days post vaccination and unsolicited AEs until 28 days post vaccination. SAEs and AESIs of confirmed HIV infection will be recorded until the end of the study. AESIs of TTS will be recorded up to Visit 23a (6 months

after the late boost vaccination). Each visit will include collection of humoral and cellular immunogenicity assays. In addition, at Visit 23a, 24 and 25 (if applicable), HIV testing will be performed, an HIV-risk assessment (see Attachment 2) will be performed and counseling related to avoidance of HIV infection will be provided to all subjects. At Visit 23 subjects will complete a social impact questionnaire (Attachment 4).

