Late Boost	7	Post-Dose 5	5	Minimum of Date and Time of the two Late Boost Injections (Day 1345 – Week 192)	Minimum of: - Maximum (28 days after late boost vaccination at 23.59, scheduled visit 4 weeks after late boost vaccination at 23:59) - 23:59 at the date of last contact (for early discontinuation)
Follow-Up 5	8			1 minute after end of Post-Dose 5 period	Minimum of: a) Last available visit for completers b) 23:59 at the date of last contact (for early discontinuation)

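### Up to 14 of the 28 days of late-boost AE follow-up may lack a scheduled enquiry: Visit 22c can validly fall on day 14, and no later routine visit is marked for AE recording

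*Protocol*

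**What the plan says.** Protocol 9.1.2 sets the boost at "Visit 22/Visit 22a: Day 1345 (Week 192) -4 weeks/+4 months" and the one-month visit at "Visit 22c*: Day 1373 ± 2 weeks (Week 196"). Post-boost visits are timed from the actual day of vaccination.

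For AEs, footnote 11 of the Time and Events Schedule for the Late Boost Extension states that "unsolicited AEs will be recorded from signing of ICF addendum for boost vaccination onwards until 28 days after boost vaccination". After vaccination, the table itself marks AE recording at Visits 22b and 22c and at the early Exit visit. It has no AE mark at 22d, 23a, 24 or 25.

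The length of the AE window is described in several ways:
- Protocol 12.3.1 gives 28 days but adds any relevant visit window.
- SAP Table 3 ends the post-dose 5 period, for subjects who do not discontinue early, at "Maximum (28 days after late boost vaccination at 23.59, scheduled visit 4 weeks after late boost vaccination at 23:59").
- SAP 5.1.1 and protocol 11.5 restrict the AE tables to 28 days after vaccination.

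SAP 5.1.4 treats a subject who reports no event as a subject without one.

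Two other late-boost endpoints depend on similar visits. Protocol 9.1.10 says that "AESIs of TTS will be recorded up to Visit 23a", while 12.3.1 asks for reporting until 6 months. The synopsis lists "Env-specific binding Abs [ELISA] at 3, 7 or 14 days and 28 days post late boost vaccination (titers and breadth") as an exploratory endpoint, and SAP 2.1 assigns samples to time points by visit number.

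**The concern.** Non-serious unsolicited AEs come to light mainly because someone asks. If the last marked enquiry takes place on day 14, an event starting on day 20 may go unrecorded, and the SAP then counts that subject as event-free. The direction of error is towards understating a primary safety endpoint.

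The SAP also shows post-dose 5 beside post-doses 1 to 4, where the 4-week visit is held to within 5 days. After doses 1 to 3 the next vaccination visit gives a further AE enquiry. The late boost has neither safeguard.

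Numbers are small. At the stated aim of 48 subjects randomized 3:1, the active arm is 48 × 3/4 = 36, so one missed subject moves an incidence by 1/36 = 2.8 percentage points.

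**Working it through.** This is calendar arithmetic. Offset = visit day − 1345, then plus or minus the window.

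1. **Nominal days.** Visit 22c: 1373 − 1345 = 28, which equals (196 − 192) × 7. Visit 23a: 1513 − 1345 = 168, which equals (216 − 192) × 7. The protocol's days reproduce exactly.

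2. **AE enquiry.** Visit 22c spans 28 − 14 = 14 to 28 + 14 = 42. Days of the 28-day window left after the visit:
   - 22c on day 14: 28 − 14 = 14 days, 14/28 = 50%
   - 22c on day 21: 28 − 21 = 7 days, 7/28 = 25%
   - 22c on day 28 or later: none
   - main-study 4-week visit at its earliest, 28 − 5 = 23: 5 days, 5/28 = 18%

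3. **Next available visit.** Visit 22d is Day 1429, so 1429 − 1345 = 84, with ± 4 weeks in the late-boost schedule: day 56 to day 112. It always falls after day 28, so one question there can close the gap. For onsets on days 14 to 28, recall would run from 56 − 28 = 28 to 112 − 14 = 98 days.

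4. **SAP period.** Table 3 takes the later of day 28 and the 4-week visit. With 22c on days 14 to 42 the period ends between day 28 and day 42. An event starting on day 35 falls inside it for a subject seen on day 42, and outside it for one seen on day 28 or earlier. SAP 5.1.1 and protocol 11.5 would leave that event out of the tables for both.

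5. **TTS.** The window comes from "1009 (Week 144), 1177 (Week 168), and 1513 (Week 216) ± 4 weeks". Visit 23a spans 168 − 28 = 140 to 168 + 28 = 196. The shortfall depends on what 6 months means:
   - 24 weeks (168 days), as the schedule labels Week 216: 0 on target, up to 28 days early (28/168 = 17%)
   - 180 days, from "Note that 1 month should be interpreted as 30 days and 1 week as 7 days": 12 on target, up to 40 days early (40/180 = 22%)

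6. **ELISA.** The 28-day sample may be drawn on days 14 to 42. The 14-day Visit 22b group is sampled on days 14 ± 3, that is 11 to 17, so the two windows overlap on days 14 to 17. At 48 subjects that group is 48 − 40 = 8.

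**The case against.** The strongest reply is that recording duties run by calendar, not by visit. Footnote 11, 9.1.10 and 12.3.1 all carry unsolicited AEs to day 28, and 9.1.10 describes the post-boost visits together, so a site could properly ask at 22d without a mark in the table. All concomitant medication up to day 28 must be recorded and medication is reviewed at 22d, so treated events may surface. SAEs are recorded throughout, and potential TTS is due within 24 hours of awareness. The 7-day solicited events end before the earliest 22c. The window is the same in the blinded placebo arm, so the comparison between arms is not biased by design. All of this stands. It limits the point to missing scheduled enquiry about non-serious unsolicited AEs, but does not supply that enquiry.

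A reader might infer more than the documents support:
- **That late events are never asked about.** The calendar-based duty rules this out.
- **That the tabulated window varies threefold, from 14 to 42 days.** This mixes the earliest enquiry with the latest period end. The Table 3 period runs 28 to 42 days, 1.5-fold at most, and the same rule applies to doses 1 to 4.
- **That an on-target Visit 23a is 12 days short for TTS.** This needs the 30-day month, which the footnote applies to the Visit 22a window. The schedule itself labels Week 216 as 6 months. Protocol 1.1.2.3 puts symptom onset usually at 1 to 4 weeks and up to 42 days, well before day 140.
- **That the ELISA timing spoils a planned comparison with Weeks 28 and 52.** SAP 6.3 specifies no such comparison for the late boost. The stated contrast by main-study group uses the same window in both groups.

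**Conclusion.** The point holds for the AE endpoint. The late-boost schedule does not guarantee enquiry across the full 28 days. The possible gap is 0 to 14 days per subject, against 0 to 5 days at the main-study 4-week visits. The upper figure is a worst case: it assumes a compliant 22c at the early edge of its window and no AE enquiry at 22d beyond what the table marks. The documents do not say how visits are expected to spread within the window, so the average gap cannot be computed. Subjects seen on or after day 28 are fully covered.

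The AE window also needs a single definition, because Table 3 and 12.3.1 allow more than 28 days while SAP 5.1.1 and protocol 11.5 do not.

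The TTS item is a wording conflict with little practical effect. The ELISA item concerns the timing of an exploratory sample, not lost follow-up. Overall this is a worthwhile, inexpensive improvement; it does not undermine the late-boost safety assessment.

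**What to change.** 1. **Protocol, AE enquiry.** Mark AE recording at Visit 22d, limited to onsets up to day 28, for subjects whose 22c fell before day 28. Alternatively, set the 22c window so that it opens no earlier than day 28. The second option avoids long recall; ± 5 days alone would still leave up to 5 days open.
2. **SAP, AE tables.** Tabulate post-dose 5 AEs by onset day 0 to 28 for every subject, and bring Table 3 and protocol 12.3.1 into line with SAP 5.1.1 and protocol 11.5. Report how many subjects had 22c before day 28.
3. **TTS.** Reconcile 9.1.10 (recording ends at Visit 23a) with 12.3.1 (until 6 months), and state what 6 months means in days.
4. **ELISA.** Present the 28-day result by actual sampling day, or add a sensitivity summary of samples at 28 ± 5 days. Protocol 9.5 already requires actual sampling dates.

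The cost is one CRF question at an existing visit, or slightly tighter scheduling of 22c, plus minor SAP programming. A retrospective question relies on recall of about 4 to 14 weeks (28 to 98 days), and some samples will fall outside the ELISA sensitivity summary. If the visits have already taken place, the SAP changes and the count in item 2 can still be made without new data.

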9.1.3. Screening Phase (Week -6 to 0)

Only healthy subjects negative for HIV infection (if possible, an assay that is FDA-approved should be selected) and complying with the inclusion and exclusion criteria specified in Section 4, Subject Population, will be included into the study. The investigator or designee will provide detailed information on the study to the subjects and will obtain written informed consent prior to each subject's participation in the study. All the procedures described in the TIME AND EVENTS SCHEDULE and TIME AND EVENTS SCHEDULE FOR OPTIONAL VECTOR SHEDDING ASSESSMENT will only take place after written informed consent has been obtained.

Screening may be conducted in part via a sponsor- and IRB/IEC-pre-approved non-study specific screening consent process, but only if the relevant pre-screening tests are identical to the per protocol screening tests and are within 6 weeks prior to first vaccination. However, no study specific procedures, other than screening assessments, will be performed until the subject has signed the study-specific ICF. The study-specific ICF date and time will be entered into the CRF. The non-study specific ICF will be considered source data.

During screening, subjects must pass the TOU, a questionnaire provided to the subject to document his/her understanding of the study (see Section 16.1 and Attachment 3). The TOU must be completed by all subjects, as the first assessment after signing of the ICF. Adaptations to the TOU are allowed for local purposes, after IRB/IEC and sponsor approval.

The following evaluations will be performed to determine eligibility requirements as specified in the inclusion and exclusion criteria:

- Medical history
- Complete physical examination, including weight and height
- Vital signs measurement
- Review of pre-study medications
- HIV-risk assessment (see Attachment 2) and counseling on avoidance of HIV infection, for both male and female subjects
- Review of inclusion/exclusion criteria
- Blood sampling for complete blood count (CBC) with differential and platelets, blood chemistry, hepatitis B/C serology, and HIV testing (including pre- and post-HIV-test counseling)
- Sexually-transmitted infection (STI) testing (syphilis, chlamydia, gonorrhea, trichomonas [trichomonas for female subjects only; urine or vaginal swab may be used])
- Contraceptive counseling for both male and female subjects
- Female subjects of childbearing potential: serum β-hCG pregnancy testing
- Urinalysis

General eligibility for this clinical study will be dependent on results of laboratory tests and the medical assessment. Study subjects who qualify for inclusion based on the medical history, physical examination, and laboratory results will be contacted and scheduled for vaccination (Visit 2) within 6 weeks from signing ICF.

Subjects with laboratory values or vital signs not meeting eligibility criteria on the screening visit may have one repeat testing during the screening period if the abnormality is not clinically significant and may be a testing aberrancy. The screening visit may be split into multiple days/visits.

After medical history, physical examination, and laboratory data have been reviewed for completeness and adherence to inclusion/exclusion criteria, the subject can be deemed to be eligible for the study.

All AEs will be recorded on the CRF, from signing of the study-specific ICF onwards, together with information about any concomitant medications.

If a subject is a screen failure, but at some point in the future is expected to meet the subject eligibility criteria, the subject may be rescreened on one occasion only. Subjects who are rescreened will be assigned a new subject number, undergo the informed consent process, and then restart a new screening phase.

Subjects who consent to the optional vector shedding assessment (see Section 9.1.8) may have baseline samples taken during screening instead of pre-vaccination on Day 1.

